17. PRIMARY OUTCOMES

17.1. PART A

The Primary objective of the **Part A** is to characterize the safety, tolerability and MTD of Givinostat in patients with PV. The determination of the MTD of Givinostat will be based on C1 DLTs.

The following primary safety parameters will be evaluated in **Part A** based on SAF analysis set:

- Number of patients experiencing adverse events.
- Type, incidence, and severity of treatment-related adverse events, graded according to Common Terminology Criteria for Adverse Events (CTCAE v. 4.03, 14th June 2010).

AEs will be coded using MedDRA dictionary (using the 20.1 version). AEs will be reported on a per patient basis. If a patient has more than one AE for a treatment that coded to the same PT, the patient will be counted only once for that PT. Similarly, if a patient has more than one AE for a treatment within a SOC category, the patient will be counted only once in that SOC category. A patient with multiple CTCAE grades for an AE will be summarised under the maximum CTCAE grade recorded for the event.

Any AE which started at or after the first administration of Study treatment (i.e. C1D1) will be considered a Treatment Emergent Adverse Event (TEAE). If the start date is missing for an AE, the AE will be considered to be a TEAE.

An overview of AEs including the number of patients with at least one AE, at least one TEAE, at least one drug-related TEAE, at least one Serious TEAE (TESAE), any SAE, any AE leading to death, any TEAE leading to death, any TEAE leading to drug discontinuation, at least one grade ≥ 3 TEAE, will be presented. The following AE frequency tables will be also provided:

Document: PPD

Author: PPD

Version Number:

V2.2

Version Date:

21 March 2018

Template No: CS_TP_BS016 – Revision 3

Reference: CS_WI_BS005

Effective Date: 01May2012

Copyright © 2012 Quintiles Transnational Corp. All rights reserved.

The contents of this document are confidential and proprietary to Quintiles Transnational Corp. Unauthorized use, disclosure or reproduction is strictly prohibited.

-
- Incidence of TEAEs by primary SOC and PT;
 - Incidence of drug-related TEAEs by primary SOC and PT;
 - Incidence of TEAEs by maximum severity, primary SOC and PT;
 - Incidence of TEAEs by strongest relationship, maximum severity, primary SOC and PT;
 - Incidence of TESAEs by primary SOC and PT;
 - Incidence of TEAEs leading to study drug discontinuation by primary SOC and PT;
 - Incidence of TEAEs leading to dose modification by primary SOC and PT.

In addition, the following primary parameter will be evaluated in **Part A** based on MTD analysis set population:

- MTD of Givinostat.

All outputs for safety outcomes will be based on the SAF analysis set, and presented by DLs (**Part A** only). There will be no planned statistical comparisons among treatment groups for safety data.

ADVERSE EVENTS

AE Investigator terms will be assigned to a PT and will be classified by primary SOC. AEs will be coded using the 20.1 version of MedDRA dictionary. TEAEs are defined as adverse events started at or after the first administration of study treatment.

See [Appendix 2](#) for handling of partial dates for AEs. In the case where it is not possible to define an AE as treatment emergent or not, the AE will be classified by the worst case (i.e. TEAE).

An overall summary of number of patients within each of the categories described in the sub-section below, will be provided as specified in the templates. Listings will include AEs and TEAEs.

A case narrative for each AE leading to treatment discontinuation (the “Action Taken with Study Drug” in section “AE” of the electronic CRF is “Definitively withdrawn”), and/or leading to death (see below), and/or ongoing at the end of treatment (the “Outcome” in the section “AE” of the electronic CRF is “Ongoing” at the time of database look) will be reported in the Clinical Study Report.

ALL TEAEs

Document PPD

Author: PPD

Version Number:

V2.2

Version Date:

21 March 2018

Template No: CS_TP_BS016 – Revision 3

Reference: CS_WI_BS005

Effective Date: 01May2012

Copyright © 2012 Quintiles Transnational Corp. All rights reserved.

The contents of this document are confidential and proprietary to Quintiles Transnational Corp. Unauthorized use, disclosure or reproduction is strictly prohibited.

Incidence of TEAEs will be presented by primary SOC and PT and also broken down further by maximum severity and relationship to Study medication.

SEVERITY AND COMMON TERMINOLOGY CRITERIA FOR ADVERSE EVENTS

AEs will be graded by the Investigators according to the Common Terminology Criteria for Adverse Events (CTCAE) version 4.03, dated 14th June 2010. The grade assigned by the Investigator will be used for this analysis.

TEAEs starting after the first dose of Study medication (i.e. C1D1) with a missing severity will be classified as “severe*” (i.e. “grade 3*”), in order to distinguish them from the TEAEs graded as severe that will be reported without “*” (i.e. “severe”).

If a patient reports a TEAE more than once within that SOC/PT, the AE with the worst severity will be used in the corresponding severity summaries.

RELATIONSHIP TO STUDY MEDICATION

In electronic CRF the relationship of an AE with the Study drug is classed as “Not Related”, “Related” or “Unknown”, based on Investigator’s judgment.

A “Related” TEAE is defined as a TEAE with a relationship to the Study medication; in this case, the Investigator ticked “Related” in the field “Relationship with Study Drug” of the section “AE” of the electronic CRF.

A “Not Related” TEAE is defined as a TEAE without a reasonable relationship to the Study medication; in this case, the Investigator ticked “Not Related” in the field “Relationship with Study Drug” of the section “AE” of the electronic CRF.

If a TEAE is reported as “Unknown” in the field “Relationship with Study Drug” of the section “AE” of the electronic CRF even after the database lock, the worst relationship will be considered (i.e. “Related*”). TEAEs with a missing relationship to Study medication even after the database lock, the worst relationship will be considered (i.e. “Related*”). In both cases, the “*” will allow to distinguish them from the TEAEs considered by the Investigators as “Related” and reported without “*” (i.e. “Related”).

If a patient reports the same TEAEs more than once within that SOC and/or PT, the TEAE with the worst case relationship to Study medication will be used in the corresponding relationship summaries.

TEAES LEADING TO DISCONTINUATION OF STUDY MEDICATION

TEAEs leading to permanent discontinuation of Study medication will be identified by using the

Document: PPD

Author: PPD

Version Number:

V2.2

Version Date:

21 March 2018

Template No: CS_TP_BS016 – Revision 3

Reference: CS_WI_BS005

Effective Date: 01May2012

Copyright © 2012 Quintiles Transnational Corp. All rights reserved.

The contents of this document are confidential and proprietary to Quintiles Transnational Corp. Unauthorized use, disclosure or reproduction is strictly prohibited.

response on “Action taken with Study Drug” ticked as “Definitively withdrawn” from the section “AE” of the electronic CRF.

For TEAEs leading to discontinuation of Study drug, summaries of incidence rates (i.e. frequencies and percentages) by SOC and PT will be presented.

ADVERSE EVENTS LEADING TO DEATH

If any patients died during the Study, as recorded on the sections “EOS” and/or “AE” of the electronic CRF, the information will be presented in a summary table and a data listing.

TEAEs leading to death will be identified by using the following responses on the section “AE” of the electronic CRF:

- “Yes” at the question “Is this a serious event?” (death details);
- “Fatal” on the field “Outcome”;
- “Death related to AE” on the field “Severity”.

A summary of TEAEs leading to death by SOC and PT will be prepared.

All details of TEAEs leading to Death (date of death, autopsy performed and date of autopsy, if applicable, and death due to of Progression of the disease), recorded on “Death report” page on eCRF, will be listed only.

A case narrative for each death will be reported in the Clinical Study Report.

DOSE LIMITING TOXICITIES

A DLT is defined as one of the following drug-related toxicity:

- Grade 4 haematological toxicities, or
- Grade 3 febrile neutropenia, or
- Grade ≥ 3 non-haematological toxicities with exception of:
 - a) Grade 3 diarrhoea without adequate supportive care lasting less than 3 days, and
 - b) Grade 3 nausea or vomiting without adequate supportive care lasting less than 3 days, or
- Any drug-related SAE, or
- Any toxicity that is clearly not related to disease progression or intercurrent illness requiring interruption of dosing for more than 3 days during the first cycle.

The severity of the above mentioned events is graded by the Investigators according to CTCAE v. 4.03,

Document: PPD

Author: PPD

Version Number:

V2.2

Version Date:

21 March 2018

Template No: CS_TP_BS016 – Revision 3

Reference: CS_WI_BS005

Effective Date: 01May2012

Copyright © 2012 Quintiles Transnational Corp. All rights reserved.

The contents of this document are confidential and proprietary to Quintiles Transnational Corp. Unauthorized use, disclosure or reproduction is strictly prohibited.

dated 14th June 2010.

Only DLTs experienced during the first cycle of treatment (i.e. up to C1D28) of **Part A** are considered for dose escalation decisions. DLTs include all AEs that are clearly not related to disease progression or intercurrent illnesses. Patients who didn't experience a DLT and missed more than 10% of the doses in Cycle 1 of **Part A** are replaced.

DLTs will be identified by using the response "Yes" at the question "Was this a Dose Limiting Toxicity Event?" on the section "AE" of the electronic CRF.

A summary of DLT by SOC and PT will be prepared.

A case narrative for each DLT will be reported in the Clinical Study Report.

SERIOUS ADVERSE EVENTS

SAEs will be identified by using the response on "Is this a serious event?" ticked as "Yes" on the "AE" section of the electronic CRF. A summary of SAE and Treatment Emergent SAEs (TESAEs) by SOC and PT will be prepared.

A case narrative for each SAE will be reported in the Clinical Study Report.

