3.5. DETERMINATION OF SAMPLE SIZE

A standard 3+3 design adopting a modified Fibonacci escalation schema is used in **Part A** [3, 4, 5].

Sample size for **Part B** is discussed for the primary endpoint defined as the Overall Response Rate after 3 cycles. Simon's 2-stage design is employed in **Part B** [6] with the aim of testing the "null hypothesis" that $RR \leq 0.50$ versus the "alternative" that $RR \geq 0.75$. Response rate was assessed as defined in paragraph 6.2.5.2 of the Study protocol version 3.0. Overall, up to 28 patients are to be recruited, 12 patients being enrolled in Stage 1. PV patients enrolled at the MTD in **Part A** can be counted towards Stage 1.

Under the "null hypothesis" (if $RR = 0.50$), the expected total sample size is 18.2 patients, the probability of early termination at the end of Stage-1 is 0.613 and the probability of rejecting the "null hypothesis" is 0.081 (the target for the type-I error being 0.100).

Under the "alternative hypothesis" (if $RR = 0.75$), the probability of rejecting the "null hypothesis" in favor of the "alternative" is 0.902 (the type-II error being 0.098).

After testing the treatment on 12 patients in Stage 1, if 6 or fewer patients responded to the treatment, the trial should be terminated rejecting the "alternative" that $RR \geq 0.75$. Otherwise, the trial should go on to Stage 2 enrolling a further 16 patients to a total of 28 patients.

If at the end of Stage-2, a total of 17 or fewer patients responded to the treatment, the "alternative hypothesis" that $RR \geq 0.75$ should be rejected; alternatively, if 18 or more patients responded, the "null hypothesis" that $RR \leq 0.50$ should be rejected.

Estimations were obtained from CRO proprietary software (based on SAS® 9.2) according to the

Document: PPD

Author: PPD

Version Number:

V2.2

Version Date:

21 March 2018

Template No: CS_TP_BS016 – Revision 3

Reference: CS_WI_BS005

Effective Date: 01May2012

Copyright © 2012 Quintiles Transnational Corp. All rights reserved.

The contents of this document are confidential and proprietary to Quintiles Transnational Corp. Unauthorized use, disclosure or reproduction is strictly prohibited.

algorithm proposed by R. Simon [6].

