16.7. SAFETY ASSESSMENTS

Safety and tolerability are evaluated by monitoring haematology and blood chemistry, urinalysis (only in the first cycle of **Part A**), by measurement of physical examination, vital signs, weight, body temperature, ECOG performance status, ECG assessment and evaluation, QTc determination and adverse events recording at scheduled times as described above. Timing information are summarised in the Study flow-chart ([Appendix A](#) of the Study protocol) and detailed in the [paragraph 4.5.4](#) of the

Document: PPD

Author: PPD

Version Number:

V2.2

Version Date:

21 March 2018

Template No: CS_TP_BS016 – Revision 3

Reference: CS_WI_BS005

Effective Date: 01May2012

Copyright © 2012 Quintiles Transnational Corp. All rights reserved.

The contents of this document are confidential and proprietary to Quintiles Transnational Corp. Unauthorized use, disclosure or reproduction is strictly prohibited.

Study protocol.

All significant findings already present during the screening visit before drug administration are reported in the appropriate section of electronic CRF, i.e. Medical History section or Current Medical Conditions section. Significant findings occurring after patient enrolment - identified as AEs - are recorded in Adverse Event section of electronic CRF.

The following criteria are used to assess the safety and tolerability both in **Part A** (primary endpoint) and after 3 and 6 cycles (primary and secondary endpoints, respectively) in **Part B**:

- Number of patients experiencing AEs.
- Type, incidence, and severity of treatment-related adverse events, graded according to Common Terminology Criteria for Adverse Events (CTCAE v. 4.03, 14th June 2010).

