Effective Date: 01May2012

Copyright © 2012 Quintiles Transnational Corp. All rights reserved.

The contents of this document are confidential and proprietary to Quintiles Transnational Corp. Unauthorized use, disclosure or reproduction is strictly prohibited.

Any AE which started at or after the first administration of Study treatment will be considered a TEAE. If the start date is missing for an AE, the AE will be considered to be treatment emergent.

An overview of AEs including the number of patients with at least one AE, at least one TEAE, at least one drug-related TEAE, at least one TESA, any SAE, any AE leading to death, any TEAE leading to death, any TEAE leading to drug discontinuation, at least one grade ≥ 3 TEAE, will be presented. The following AE frequency tables will be also provided:

- Incidence of TEAEs by primary SOC and PT;
- Incidence of drug-related TEAEs by primary SOC and PT;
- Incidence of TEAEs by maximum severity, primary SOC and PT;
- Incidence of TEAEs by strongest relationship, maximum severity, primary SOC and PT;
- Incidence of TESAEs by primary SOC and PT;
- Incidence of TEAEs leading to study drug discontinuation by primary SOC and PT;
- Incidence of TEAEs leading to dose modification by primary SOC and PT.

The primary safety parameters will be evaluated in **Part B after 3 cycles of treatment** (i.e. at the end of Cycles 3, or including data related to Cycles 1, 2 and 3) based on SAF analysis set and taking into account the same rules describes in the paragraphs [17.1](#).

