APPENDIX 2. PARTIAL DATE CONVENTIONS

Imputed dates will NOT be presented in the listings.

ALGORITHM FOR TREATMENT EMERGENCE OF ADVERSE EVENTS

START DATE	STOP DATE	ACTION
Known	Known	If start date < study med start date, then not TEAE If start date >= study med start date, then TEAE
	Partial	If start date < study med start date, then not TEAE If start date >= study med start date, then TEAE
	Missing	If start date < study med start date, then not TEAE If start date >= study med start date, then TEAE
Partial, but known components show that it cannot be on or after study med start date	Known	Not TEAE
	Partial	Not TEAE
	Missing	Not TEAE
Partial, could be on or after study med start date	Known	If stop date < study med start date, then not TEAE If stop date >= study med start date, then TEAE
	Partial	Impute stop date as latest possible date (i.e. last day of month if day unknown or 31st December if day and month are unknown), then: If stop date < study med start date, then not TEAE If stop date >= study med start date, then TEAE

Document: PPD

Author: PPD

Version Number:

V2.2

Version Date:

21 March 2018

Template No: CS_TP_BS016 – Revision 3

Reference: CS_WI_BS005

Effective Date: 01May2012

Copyright © 2012 Quintiles Transnational Corp. All rights reserved.

The contents of this document are confidential and proprietary to Quintiles Transnational Corp. Unauthorized use, disclosure or reproduction is strictly prohibited.

START DATE	STOP DATE	ACTION
	Missing	Assumed TEAE
Missing	Known	If stop date < study med start date, then not TEAE If stop date >= study med start date, then TEAE
	Partial	Impute stop date as latest possible date (i.e. last day of month if day unknown or 31st December if day and month are unknown), then: If stop date < study med start date, then not TEAE If stop date >= study med start date, then TEAE
	Missing	Assumed TEAE

ALGORITHM FOR PRIOR/CONCOMITANT MEDICATIONS AND PRIOR/CONCOMITANT NON-DRUG THERAPIES:

START DATE	STOP DATE	ACTION
Known	Known	If stop date < study med start date, assign as prior If stop date >= study med start date and start date <= end of treatment, assign as concomitant If stop date >= study med start date and start date > end of treatment, assign as post study

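### An AE with a missing start date but a stop date before the first dose is a TEAE under Sections 17.1, 17.2 and 18.2 and not a TEAE under Appendix 2, and no precedence is stated

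*SAP*

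**What the plan says.** Section 17.1 (Part A, primary outcomes) defines a TEAE as an AE that started at or after the first administration of study treatment, and then adds "If the start date is missing for an AE, the AE will be considered to be a TEAE". Section 17.2 (Part B, primary outcomes) has the equivalent: "If the start date is missing for an AE, the AE will be considered to be treatment emergent". Section 18.2 (Part B, secondary outcomes) uses the same sentence as 17.1. None of the three mentions the stop date.

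The adverse-events text later in 17.1 refers the reader to Appendix 2 "for handling of partial dates for AEs". It keeps a worst-case rule for cases where "it is not possible to define an AE as treatment emergent or not, the AE will be classified by the worst case (i.e. TEAE").

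The treatment-emergence algorithm in Appendix 2 has three rows for a missing start date:

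- Stop date known: "If stop date < study med start date, then not TEAE"; otherwise TEAE.
- Stop date partial: the latest possible stop date is imputed and the same test applies.
- Stop date missing: assumed TEAE.

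**The concern.** The same event is in the TEAE tables under one part of the SAP and out under another. Two programmers working independently from this document could produce different tables and both be following it. The unconditional sentence also gives a result that the SAP's own definition rules out, because an event that ended before the first dose cannot have started at or after it.

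Two outputs are at stake. The first is the set of TEAE tables, which belong to the primary safety reporting of both parts. The second is the drug-related TEAE table. Under 17.1, a TEAE whose relationship is still unknown or missing after database lock is reported as `Related*`, so a poorly recorded pre-dose event could be shown as drug-related.

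**Working it through.** **Step 1. Compare the two rules.** For an AE with a missing start date there are five stop-date cases:

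| Stop date | 17.1, 17.2, 18.2 | Appendix 2 | Agree? |
|---|---|---|---|
| Known, before first dose | TEAE | Not TEAE | No |
| Known, on or after first dose | TEAE | TEAE | Yes |
| Partial, latest possible date before first dose | TEAE | Not TEAE | No |
| Partial, latest possible date on or after first dose | TEAE | TEAE | Yes |
| Missing | TEAE | TEAE | Yes |

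The rules disagree in 2 of 5 cases. Both are events shown to have ended before dosing.

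**Step 2. Look for a precedence rule.** There is none. The reference from 17.1 to Appendix 2 is worded for partial dates, whereas the conflict concerns missing ones. The worst-case rule in 17.1 applies only when emergence cannot be determined. For an event with a pre-dose stop date it can be determined, so this text sides with Appendix 2 against the unconditional sentence in the same section.

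**Step 3. Can such an event be recorded as an AE?** Yes. Section 16.7 says "Significant findings occurring after patient enrolment - identified as AEs - are recorded in Adverse Event section of electronic CRF", and Section 3.1 places enrolment confirmation before the first drug intake. The AE overview in 17.1 counts patients with at least one AE separately from those with at least one TEAE, so it allows for AEs that are not treatment-emergent.

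**Step 4. Size per affected patient.** The Part B denominators are in Section 3.5: "Overall, up to 28 patients are to be recruited, 12 patients being enrolled in Stage 1". Table 1.1 splits DL1 into two columns of three patients, and Section 3.7 gives three patients at DL6. If the patient has no other TEAE in the row, the incidence moves by 1/n:

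- Part B overall: 1/28 = 3.6 percentage points
- Part B Stage 1: 1/12 = 8.3 percentage points
- A three-patient Part A column: 1/3 = 33.3 percentage points

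The condition matters because each patient is counted once per preferred term and once per SOC. If the patient has another TEAE in that row, the shift is zero.

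**The case against.** The strongest reply is that the SAP already points to Appendix 2. Section 17.1 cites it, 17.2 and 18.2 adopt the rules of 17.1, and Appendix 2 has explicit rows for a missing start date under a heading about treatment emergence. Section 6.1 also links Appendix 2 to partial or missing event dates, though only for study day and durations. A programmer might well read the body sentence as shorthand. That is a fair reading, but it has to be inferred: the reference in 17.1 covers partial dates only, and the unconditional sentence appears three times.

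The case is also narrow. Findings already present at screening go to medical history. An affected AE must therefore be recorded between enrolment and first dose, and have a usable stop date but no start date at all. This stands, and zero affected events is quite possible. In 18.2 the practical effect is smaller still, because that section limits its TEAEs to those starting after the first administration of Cycle 4.

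A reader might infer three stronger consequences that the document does not support:

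- *That a missing severity would push such an event into the grade 3 or higher tables.* Section 17.1 limits the `severe*` imputation to TEAEs starting after the first dose. An event that ended before that dose does not meet this condition, so the consequence is not established.
- *That the primary safety outcomes as a whole are affected.* The first listed parameter is the number of patients with AEs, not TEAEs, and this rule does not change it. The second concerns treatment-related AEs. It is touched only if the event is recorded as related, or its relationship is unknown or missing.
- *That dose selection could be affected.* DLTs are identified from a CRF question, not from the TEAE flag.

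**Conclusion.** The contradiction is real and follows from the text alone. The unconditional sentence in 17.1, 17.2 and 18.2 conflicts with Appendix 2, and with the SAP's own TEAE definition, for events known to have ended before the first dose. Such an event could be counted as a TEAE and, with an unknown or missing relationship, as `Related*`. The asterisk would keep that imputation visible.

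The practical weight is low. The error can only add events, so it is conservative for safety, and the MTD/DLT result does not depend on it. The figures of 3.6, 8.3 and 33.3 percentage points are per affected patient. They assume the planned denominators and no other TEAE in the row. The SAP gives no count of affected events. This is a minor wording correction.

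**What to change.** In 17.1, 17.2 and 18.2, replace the sentence on missing start dates with: *If the start date is missing or partial, treatment emergence is determined by the algorithm in Appendix 2.*

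Add no further clause. A gloss saying that only events not shown to have ended before the first dose count as TEAEs would create a new conflict. Appendix 2 makes an event not a TEAE when the known parts of its partial start date place it before dosing, whatever its stop date. If that event were still ongoing after dosing, the gloss would count it.

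The cost is three wording edits. The algorithm is already specified, so no new derivation is needed.

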Frequency and percentage of patients in each response category (CR, PR and NR rate for PV and ET; CCR, major response, moderate response, minor response and NR rate for MF) will be presented at C6D28. Of note, patients who dropped the study due to drug-related TEAE(s) before that the post-baseline efficacy measurement is obtained (i.e. at C3D28 and/or at C6D28), the post-baseline efficacy measurements (i.e. at C3D28 and/or at C6D28) will be considered as “No Response*”, even if these assessments were not performed. “*” will allow to distinguish them from them from the therapeutic response evaluation result of “No Response”, that will be reported without “*” (i.e. “No Response”). Other missing data will not be replaced, if not otherwise specified.

The following secondary safety parameter will be evaluated in **Part B after 6 cycles of treatment** (i.e. at C6D28, or including data related to Cycle 4 Day 28 (C4D28), Cycle 5 Day 28 (C5D28) and any unscheduled visit included in that interval period) based on SAF analysis set:

- Number of patients experiencing AEs.
- Type, incidence, and severity of treatment-related AEs, graded according to CTCAE v. 4.03 (14th June 2010).

AEs will be coded using MedDRA dictionary (using the 20.1 version). AEs will be reported on a per patient basis. If a patient has more than one AE for a treatment that coded to the same PT, the patient will be counted only once for that PT. Similarly, if a patient has more than one AE for a treatment within a SOC category, the patient will be counted only once in that SOC category. A patient with multiple CTCAE grades for an AE will be summarised under the maximum CTCAE grade recorded for the event.

Any AE which started at or after the first administration of study treatment will be considered a TEAE. If the start date is missing for an AE, the AE will be considered to be a TEAE.

TEAE included in this analysis are defined as those starting after the date of the first administration of Cycle 4.

An overview of AEs including the number of patients with at least one AE, at least one TEAE, at least one drug-related TEAE, at least one TESAE, any SAE, any AE leading to death, any TEAE leading to death, any TEAE leading to drug discontinuation, at least one grade ≥ 3 TEAE, will be presented. The following AE frequency tables will be also provided:

- Incidence of TEAEs by primary SOC and PT;
- Incidence of drug-related TEAEs by primary SOC and PT;

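### The TEAE rule uses the onset date only, so an AE that begins before the first dose and worsens on Givinostat under the same record falls outside the TEAE tables

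*SAP*

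**What the plan says.** The definition is given in three sections of the SAP and made operational in Appendix 2.

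- Section 17.1 (Part A, adverse events): "TEAEs are defined as adverse events started at or after the first administration of study treatment".
- Section 17.2 (Part B, 3 cycles): "Any AE which started at or after the first administration of Study treatment will be considered a TEAE".
- Section 18.2 (Part B, 6 cycles): "Any AE which started at or after the first administration of study treatment will be considered a TEAE". The same section then narrows the window, again by onset: "TEAE included in this analysis are defined as those starting after the date of the first administration of Cycle 4".
- Appendix 2, for a known start date: "If start date < study med start date, then not TEAE". This line stands for known, partial and missing stop dates alike. A partial start date that can only fall before dosing is also classed as not a TEAE.

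Two other rules bear on the point. Section 17.1 has a worst-case fallback to TEAE, but it applies only where status cannot be determined. Section 17.1 also says of severity: "A patient with multiple CTCAE grades for an AE will be summarised under the maximum CTCAE grade recorded for the event".

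Section 16.7 sends significant findings already present at the screening visit to the medical history or current conditions sections of the CRF. Findings that arise after enrolment go to the AE section. Section 16.10 refers to the protocol for AE definitions, coding and reporting.

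**The concern.** A treatment-emergent definition normally has two limbs: new onset after dosing, and worsening after dosing of something already present. This SAP has only the first. The overview counts patients with at least one AE separately from patients with at least one TEAE, so the plan expects some AEs to start before the first dose. If one of these worsens on drug within its own record, the Appendix 2 rule still looks at the original start date.

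Safety and tolerability is a primary outcome in both parts, and the type, incidence and severity of treatment-related AEs are reported through TEAE-based tables. Any loss goes one way, towards fewer events attributed to the treatment period.

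Outputs could also disagree. DLTs come from a CRF tick box, so an event could be summarised as a DLT in Part A and be missing from the drug-related TEAE table. Narratives cover each AE leading to discontinuation, while the matching table covers only TEAEs.

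The rule also sits oddly with the SAP's caution elsewhere. Section 17.1 treats a missing severity as grade 3 and an unknown relationship as related, yet documented worsening on drug is not counted.

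**Working it through.** The SAP states no figure on this point, so there is nothing to reproduce. The check applies the rule to test records and then works out what one patient is worth in each denominator.

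**1. Is there a worsening clause?** The definitions in 17.1, 17.2 and 18.2 and the Appendix 2 table all turn on start date. None mentions an increase in grade. The worst-case fallback does not help: a known pre-dose start is a determined case, and the determination is not TEAE.

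**2. Test records (first dose on Day 1).**

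| Onset | Grade increase | SAP rule (onset on or after Day 1) | Onset, or grade increase, on or after Day 1 |
|---|---|---|---|
| Day -3 | Day 20 | not TEAE | TEAE |
| Day 1 | Day 20 | TEAE | TEAE |
| Day 20 | Day 20 | TEAE | TEAE |

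The rules differ only in the first row.

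**3. When can the first row occur?** Two conditions are needed.

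- The AE must have been recorded between enrolment and the first dose. By section 16.7, something already present at the screening visit goes to medical history instead.
- The worsening must stay on the original record. If the site enters it as a new AE, that record has its own on-treatment start date and is a TEAE. The maximum-grade sentence in 17.1 allows several grades under one event but does not establish that records are kept that way.

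**4. Where would such an event be missing, and where would it remain?**

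- Missing: the tables of TEAEs by SOC and PT, drug-related TEAEs, TEAEs by maximum severity and by relationship, serious TEAEs, and TEAEs leading to discontinuation or dose modification; also the overview rows built on TEAEs, including grade 3 or above.
- Still present where applicable: the overview rows for any AE, any SAE and any AE leading to death; the all-SAE summary; DLTs; AE listings; narratives; and the laboratory shift tables and platelet bands of sections 20.1 and 20.2.

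**5. Value of one patient.** The reduction in a row is k/n, where n is the number treated and k is the number of affected patients with no other qualifying TEAE in that row. The values of n come from sections 3.4.1, 3.5, 3.7 and 4.

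- Part B: 1/28 = 3.6 percentage points
- Part B Stage 1: 1/12 = 8.3 points
- DL1 with its expansion: 1/6 = 16.7 points
- A three-patient dose level: 1/3 = 33.3 points

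The SAP gives no k. Assuming 0 to 3 such patients of 28, the range is 0 to 3/28 = 10.7 points.

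**6. A related effect in 18.2.** The 6-cycle safety tables select on onset after the first Cycle 4 dose. An event that starts in Cycle 2 and worsens in Cycle 5 on one record is therefore outside that window, although it is a TEAE overall.

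**The case against.** The strongest reply is that the loss depends on recording practice, which section 16.10 leaves to a protocol section not at hand. If that section requires any worsening to be entered as a new AE, nothing drops out. The SAP text is compatible with this: its severity rule in 17.1 speaks of a patient reporting a TEAE more than once within a SOC/PT and taking the worst report, which fits one grade per record. This stands as a limit on impact. It does not remove the gap in the definition, because treatment emergence is an analysis rule that the SAP fixes itself, and the SAP does not say that worsening generates a new record.

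The reply is also right about the exposure window. A reader might infer that every event arising during the roughly 28 days of screening is at risk. The document does not support that: by section 16.7, AE recording starts after enrolment, and findings present at screening go to medical history. The enrolment-to-first-dose interval is not given.

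A reader might further infer that a pre-dose event can never count as a TEAE, or that the MTD is affected. Neither follows. With a missing start date, or a partial one that could fall on or after dosing, Appendix 2 uses the stop date or assumes TEAE. DLTs, and so the MTD, come from a CRF tick box. The first primary safety parameter counts patients with AEs, not TEAEs. Thrombocytopenia, which the SAP singles out in section 3.7, is also captured through the laboratory tables.

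**Conclusion.** The point holds in conditional form. The rule as written returns not TEAE for an AE with a known or clearly pre-dose start, whatever happens to its grade on drug. If such an AE worsens on Givinostat within the same record, it is absent from the TEAE-based tables, while the outputs that do not use the TEAE rule still carry it.

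The size is 3.6, 8.3 or 33 percentage points per affected patient for denominators of 28, 12 or 3, provided the patient has no other qualifying TEAE in that row. These are illustrations for one patient, not estimates of bias. The count of such events is unknown and may be zero, so the document does not show that toxicity is in fact under-counted. It shows a rule that could only err in that direction and is easily closed.

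**What to change.** In sections 17.1, 17.2 and 18.2 and in Appendix 2, define a TEAE as an AE that starts on or after the first dose, or that was present before the first dose and increases in CTCAE grade on or after it. State how the date is set: where worsening is entered as a new AE record, its own start date applies; otherwise use the date of the higher grade.

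In the severity tables, use the maximum grade on treatment rather than the maximum recorded for the event, so that a pre-dose grade cannot be reported as on-drug severity.

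In 18.2, also state whether an event that began earlier and worsens after the first Cycle 4 dose belongs in the 6-cycle tables.

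The cost is SAP wording and one programming condition. The small downside is that a few data queries may be needed where a grade-change date was not entered; the SAP does not show whether the eCRF holds these dates.
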